4.1. Overall Design

- A multi-center, randomized, open (with partial blinding for outcome assessments), parallel-group, superiority study.
- Study intervention assignment: 1:1 by central computer randomization at the time of inclusion, stratified by country.
- Treatment strategies compared:
 - Administration of TNFi based on proactive TDM (TDM group)
 - Administration of TNFi according to standard of care without knowledge of serum drug levels or ADAb status (Standard of care group)
- Population: Adult patients with RA in DAS28-CRP remission or low disease activity (DAS28-CRP < 3.2) on therapy with a SC TNFi (adalimumab) in standard dose for 3–24 months and an indication for continuation of treatment according to the treating physician.
- Algorithm for dose adjustments: In the TDM group, adjustments of the dosing interval of the TNFi are made according to a predefined algorithm, with the aim of reaching and maintaining a serum drug level within the therapeutic range.
- Duration of study: The randomized treatment strategy will be continued for the duration of the follow-up period (18 months).
- Study visits: Onsite visits 0, 4, 8, 12, and 18 months. Additional digital visits and onsite blood sampling at 2, 6, 10, 14, and 16 months.
- Primary endpoint: sustained disease control without disease flare during the follow-up period of 18 months.
 - In order to identify the primary endpoint, each study center will have a phone number for participants to call in case of increased disease activity. If a participant is experiencing a potential flare, a visit will be arranged within one week after contacting the study center to allow for a thorough examination and documentation of disease status.
- Participants experiencing a flare (primary endpoint) will be followed according to the visit scheme. Further therapy will be at the discretion of the treating physician, but for participants in the TDM group, an increase in dose will be recommended if the drug level is low (according to the TDM algorithm).
- Participants who are switched to another treatment during the study will still be followed according to the visit scheme but without TDM.
- Biosimilars: Switching between biosimilar drugs is allowed at any time during the study.

4.2. Scientific Rationale for Study Design

Study design: A randomized superiority trial is the preferred study design to assess an intervention suggested to improve clinical outcomes.

Masking: Due to the need for communication between study personnel and participants regarding dose changes in the TDM group, blinding of study personnel and participants is not feasible. To mitigate the risk of expectation bias, joint count assessor (component of the primary outcome) will be blinded.

Primary endpoint: To maintain sustained disease control is the treatment target in RA care (3). Preventing flares may improve quality of life, delay disease progression, and avoid irreversible organ damage, which can make a great difference to a large number of patients with RA (19, 20, 35, 36). There is no consensus on the definition of flare in RA. The definition of a flare used in the present study is based on work conducted within Outcome Measures in Rheumatology (OMERACT) on the minimally clinically important difference and minimally detectable difference of DAS28-CRP, and definitions used in prior randomized controlled trials (RCTs) within this field (33, 37-40).

Eligibility: Inclusion criteria are wide in order to improve external validity.

4.2.1. Patient Input into Design

Three user representatives with RA were consulted in an early phase of planning this study and during protocol development. They gave input on the interventions, study outcomes, and study duration. Additionally, they gave specific input to the informed consent form and the patient information letter. The user representatives will continue their involvement during the continuation of the study.

4.3. Justification for the Choice of Study Drug and the TDM Strategy

As knowledge of the therapeutic ranges at this point is most robust for adalimumab, and since adalimumab is currently by far the most used SC TNFi, the study protocol has been developed with the aim of including RA patients on therapy with adalimumab. In case of evidence regarding therapeutic ranges for other SC TNFi emerge and their clinical use increase during the study period, RA patients on other SC TNFi will be considered for inclusion following a protocol amendment.

The treatment algorithm in the TDM group is based on an extensive literature review, assessment of new unpublished data, and expert opinions. It has been developed through a series of meetings in the project group including international leading experts in this field (both clinicians experienced with TDM and laboratory physicians).

There are strong indications that the lower limit of the therapeutic range of adalimumab in RA is close to 5 mg/L (7, 23, 41-44), and data indicate that an upper limit is around 12 mg/L (7, 23, 42).

The dose alterations recommended by the algorithm were based on literature review and on considerations of feasibility and expert opinion (44-47). The cut-off for ADAb leading to

change of therapy is based on clinical experience and is the same as the cut-off used in an equivalent assay for the TNFi infliximab in the previous NOR-DRUM trials (32, 33).

4.4. End-of-Study Definition

A participant is considered to have completed the study when the participant has completed the visit at 18 months. The end of the study is defined as the date of the last visit of the last participant in the study.

5. Study Population

Prospective approval of protocol deviations to recruitment and enrolment criteria, also known as protocol waivers or exemptions, is not permitted.

5.1. Inclusion Criteria

Participants are eligible to be included in the study only if *all* of the following criteria apply:

1. A clinical diagnosis of RA
2. ≥ 18 and < 75 years of age at screening
3. On stable therapy with standard dose of a SC TNFi (adalimumab) for a minimum of 3 months and a maximum of 24 months
4. In low disease activity or remission (DAS28-CRP < 3.2) and indication for continuation of treatment according to the treating physician
5. Subject capable of understanding and signing an informed consent form

5.2. Exclusion Criteria

Participants are excluded from the study if *any* of the following criteria apply:

1. Major comorbidities, such as previous malignancies within the last 5 years, uncontrolled diabetes mellitus, severe infections (including HIV), uncontrollable hypertension, severe cardiovascular disease (NYHA class 3 or 4), severe respiratory diseases, demyelinating disease, significant chronic widespread pain syndrome, significant renal or hepatic disease, and/or other diseases or conditions which either contraindicate treatment with SC TNFi or make adherence to the protocol difficult
2. Hypersensitivity to SC TNFi (adalimumab)
3. Pregnancy, or subject considering becoming pregnant during the study period
4. Psychiatric or mental disorders, alcohol abuse or other substance abuse, language barriers, or other factors that makes adherence to the study protocol difficult
5. Changes in csDMARD co-medication, including dose changes of csDMARD or changes in the dose of corticosteroids within the last 2 months
6. Co-medication with bDMARD, tsDMARD, or other immunosuppressive drugs (excluding csDMARD and corticosteroids ≤ 7.5 mg prednisolone (or equivalent) once daily).
7. Active participation in any other interventional study
8. In need of live vaccines during the study period

5.3. Lifestyle Considerations

Not applicable.

5.4. Screen Failures

A screen failure occurs when a participant who has consented to participate in the clinical study is not subsequently entered in the study. A minimal set of screen failure information is

required to ensure transparent reporting of screen failure participants to meet the Consolidated Standards of Reporting Trials (CONSORT) publishing requirements and to respond to queries from regulatory authorities. Minimal information includes demography, screen failure details and eligibility criteria.

Individuals who do not meet the criteria for participation in this study (screen failure) may be rescreened (maximally two times) under a new participant number for every screening/rescreening event.

A list of pre-screened patients not eligible for screening will be kept with the patient identification list and will describe age, gender and reason for not eligible for screening.

5.5. Criteria for Temporarily Delaying

Not applicable.

6. Study Intervention and Concomitant Therapy

Study interventions are all pre-specified investigational and non-investigational medicinal products, medical devices, and other interventions (e.g., surgical and behavioral interventions) intended to be administered to the study participants during the study conduct.

Participants enrolled in the RA-DRUM trial are on therapy with SC TNFi.

They are randomized 1:1 to either:

- Administration of SC TNFi based on proactive TDM (TDM group)
- Administration of SC TNFi according to standard of care without knowledge of serum drug levels or ADAb status (Standard of care group)

If the participants are using prednisolone (≤ 7.5 mg prednisolone oral dose or equivalent) or concomitant csDMARD including methotrexate, sulfasalazine, hydroxychloroquine, or leflunomide in any dose this will be continued in an unchanged dose.

6.1. Study Intervention Administered

6.1.1. The TDM Group

In the TDM, the SC TNFi dose will be adjusted according to the algorithms outlined in Table 1 in order to keep the drug level within the therapeutic range.

Prior to a dose change, the study personnel must check by a phone call to the participant if the drug has been administered according to the treatment algorithm (as defined in Table 1) or if injections have been postponed or dropped due to medical or other reasons.

The following exceptions from the algorithm in Table 1 are recommended if the drug has not been administered according to the treatment algorithm during the last month:

- If the drug level is low with no or low ADAb and there has been a pause in medication of more than 1 week for the last month prior to the blood sampling the dose should be kept stable
- If the drug level is high and the participant has taken the injection in a higher dose or more frequent than prescribed, the dose should be kept stable.

The reason for pause in therapy should be recorded in the eCRF.

In the TDM group, results for drug levels and ADAb will be reported to the investigators via the eCRF within 10 days after receiving the sample. Results in the standard care group will be recorded in the eCRF but not accessible to study personnel, and transferred to the PI upon conclusion of the clinical trial.

Table 1. Study Intervention

	Adalimumab	x	y	z
Trade name(s)	Originator and all approved adalimumab biosimilars*			
Type	Biologic drug			
Dose Formulation	Subcutaneous (SC) injection			
Recommended Dose**	40 mg SC every 14 days, if necessary 40 mg SC every 7 days or 80 mg SC every 14 days			
IMP and NIMP	IMP			
Drug target range	5.0-12.0 mg/L			
Cut-off ADAb high levels	> 50 µg/L			
TDM strategy				
• Within target range	Keep dose			
• Low drug levels, ADAb undetectable or low levels	Decrease dosing interval by one week to a maximum of 40 mg/week			
• Low drug levels, ADAb high levels	Switch to another therapy			
• High drug levels	Increase dosing interval by one week up to a maximum of 6 weeks			

* All adalimumab biosimilars approved by the European Medicines Agency
**According to the Summary of Product Characteristics (SmPC)
ADAb = anti-drug antibodies; TDM = Therapeutic drug monitoring
X,y,z: The protocol has been developed with the aim of including RA patients on therapy with adalimumab. If sufficient evidence emerges regarding therapeutic ranges of other SC TNFi during the study period, it will be considered to amend the protocol to include RA patients on other SC TNFi.

6.1.2. The Standard of Care Group

In participants randomized to the Standard of care group, the SC TNFi will be administered according to standard of care without knowledge of serum drug levels or ADAb at all visits throughout the study. Results of serum drug levels and ADAb testing in the Standard of care group will be kept hidden from the investigators.

6.1.3. Both Groups

In order to identify the primary endpoint, each study center will have a phone number for participants to call in case of increased disease activity. If a participant is experiencing a potential flare, a visit will be arranged within one week after contacting the study center to allow for a clinical examination and documentation of disease status.

Participants with a flare (primary endpoint) will be followed according to the visit scheme. Further therapy will be at the discretion of the treating physician, but for participants in the TDM group, an increase in dose will be recommended if the drug level is low (according to the TDM algorithm).

If SC TNFi is terminated due to any reason, the participant will still be included in the study and followed with study visits according to the planned visit schedule. The reason for termination of therapy should be recorded in the eCRF. If SC TNFi is terminated due to AE, the choice of treatment should be at the discretion of the investigator. Participants who are

switched to another treatment during the study will still be followed according to the visit scheme. Switching between biosimilar drugs is allowed at any time during the study.

6.2. Preparation, Handling, Storage, and Accountability

Participants will be prescribed the TNFi and receive it from the pharmacy as per usual routine use. Participants will handle, store, and administer the drug according to the SmPC. This includes following the expiry date on the packaging and keeping the drug cool during storage. The IMP has already been placed on the market as an authorized medicinal product in accordance with Directive 2001/83/EC and Regulation (EC) No 726/2004 of the European Parliament and of the Council, and there is no blinding of the IMP. Therefore, no additional labelling will be applied.

6.3. Assignment to Study Intervention

On the day of enrolment, participants will be assigned a unique randomization number in ascending numerical order at each study site. The randomization number encodes the participant's assignment to one of the two treatment groups of the study according to the randomization schedule. Once a randomization number has been assigned, it may not be reassigned.

Eligible participants will be allocated in a 1:1 ratio between TDM and Standard of care using a permuted block randomization procedure stratified by country (N=3), using random block sizes. Details of block size and allocation sequence generation will be kept in a separate document unavailable to those who enroll participants or assign treatment.

The computer-generated allocation sequence will be incorporated into the eCRF system and made available to site personnel. The allocation will not be available until the participant has signed the informed consent form and deemed eligible to participate in the study. That is, study personnel will only know the treatment allocation of included participants, but not of future participants.

6.4. Masking

This is an open-label study; potential bias will be reduced by the following step:
Blinded assessment of part of the primary outcome (joint count).

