Endpoints	
Primary endpoint: Sustained disease control over the follow-up period of 18 months without flare, with flare defined as either of the following:
 
 • A combination of an increase in Disease Activity Score using 28 joints C-reactive protein (DAS28-CRP) > 1.2, or > 0.6 if DAS28-CRP ≥ 3.2, AND ≥ 2 swollen joints on examination of 44 joints

	
 • Consensus between patient and physician that a disease flare has occurred, leading to a major change in treatment 
If more than one TNFi type are included, subgroup analyses according to each TNFi type used will be performed.
 
Secondary endpoints:
 
 • Disease activity at 4, 8, 12, and 18 months assessed by DAS28-CRP, Evaluators Global Assessment of Disease Activity (EGA), Clinical Disease Activity Index (CDAI), Simple Disease Activity Index (SDAI), American College of Rheumatology (ACR)/European Alliance of Associations for Rheumatology (EULAR) remission criteria, Rheumatoid Arthritis Impact of Disease (RAID), Modified Health Assessment Questionnaire (MHAQ), biochemical parameters • Time to disease flare • Number and type of adverse events (AEs) • Drug survival, drug consumption, occurrence of ADAbs, serum drug levels
Overall Design	
A multicenter, randomized, two-arm, parallel-group, open, superiority trial where adult participants with RA in DAS28-CRP remission or low disease activity (DAS28-CRP < 3.2) on therapy with standard dose of a SC TNFi (adalimumab) for 3-24 months with indication for continuation of treatment according to the treating physician are stratified by country and allocated 1:1 to:
 
 • Administration of TNFi based on proactive TDM (TDM group) • Administration of TNFi based on standard of care without knowledge of serum drug levels or ADAbs status (Standard of care group) 
The protocol has been developed with the aim of including RA patients on therapy with adalimumab. If sufficient evidence emerges regarding therapeutic ranges of other SC TNFi during the study period, it will be considered to amend the protocol to include RA patients on other SC TNFi.

Visit Frequency	Onsite visits will be conducted at 0, 4, 8, 12, and 18 months following randomization, with additional digital visits and blood sampling at 2, 6, 10, 14, and 16 months.
Study Duration	18 months
Number of Participants	A minimum of 350 patients will be enrolled.

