8.2.2. Definition of Flare

A flare is defined as a combination of an increase in DAS28-CRP of 1.2 units, or 0.6 if DAS28-CRP \geq 3.2, AND at least 2 swollen joints on examination of 44 joints (39, 40, 53).

If a participant does not fulfil the formal definition, but experiences a clinically significant worsening, according to both the investigator and participant, that leads to a major change* in treatment, this should be considered as a flare but be recorded separately in the eCRF.

*A major change in treatment includes:

- Switching to another bDMARD or a tsDMARD
- Adding a csDMARD
- Increasing the dose of a concomitant csDMARD
- Adding or increasing systemic glucocorticoids (per orally, intravenous or intramuscular)
- Receiving more than one intra-articular glucocorticoid injection at one visit
- Shortening the interval of the SC TNFi for clinical reasons (Standard of care group)

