9.3.2.2. Sensitivity Analysis

Sensitivity analyses will include additional approaches to dealing with missing values of the primary endpoint, possibly including, but not limited to, complete-case analysis, last-observation carried forward imputation, and worst-case imputation (i.e., imputing missing values as flare). Additional analyses may include adjustment for unbalanced baseline covariates such as age, sex, and co-medication.

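### The only masking step, a blinded joint count, does not reach the consensus route to flare, and no analysis named in the protocol shows the primary comparison without that route

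*Protocol*

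**What the plan says.** **Masking.** Section 4.2 states that "blinding of study personnel and participants is not feasible" and that, against expectation bias, the "joint count assessor (component of the primary outcome) will be blinded". Section 6.4 lists the same single step: "Blinded assessment of part of the primary outcome (joint count".

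**Primary event.** Sections 1.1, 3 and 8.2.2 define flare by either of two routes.

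- *Formal route:* a rise in DAS28-CRP above 1.2, or above 0.6 if DAS28-CRP is at least 3.2, "AND at least 2 swollen joints on examination of 44 joints".
- *Consensus route:* "Consensus between patient and physician that a disease flare has occurred, leading to a major change in treatment". Section 8.2.2 applies it when the formal definition is not met, and says that "this should be considered as a flare but be recorded separately in the eCRF".

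**Qualifying changes.** Sections 3 and 8.2.2 list the major changes. All apply to both arms except the last: "Shortening the interval of the SC TNFi for clinical reasons (Standard of care group". Section 3 has the same restriction, worded as a dose increase. Sections 4.1 and 6.1.3 recommend a dose increase in the TDM group after a flare if the drug level is low. That step is not on the list of major changes.

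**Analyses.** Section 9.3.2.2 begins "Sensitivity analyses will include additional approaches to dealing with missing values of the primary endpoint" and adds optional covariate adjustment. Section 9.3.2.3 is a Cox model of time to first flare, and 9.3.2.4 is a subgroup analysis by TNFi type. All use the composite flare.

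**The concern.** For a consensus-only flare the formal criterion has, by definition, not been met. The blinded joint count therefore did not decide the event. Two people who know the allocation did, one by reporting the worsening and the other by agreeing and changing treatment. The safeguard does not cover one of the two sufficient routes to the primary event.

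The arm-specific trigger adds a difference that does not depend on anyone's expectations. Take a clinically meaningful worsening that misses the formal definition and is answered only by more TNFi. In the Standard of care group this is a flare. In the TDM group the list as written does not make it one. The direction favors TDM.

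If a benefit were seen, a reader would want to know how much of it came from formal flares, how much from consensus flares, and how much from the one-arm trigger. The separate eCRF record makes the first split possible, but nothing in section 9 asks for it.

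**Working it through.** **1. The two routes side by side**

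| | Formal route | Consensus route |
|---|---|---|
| Blinded joint count required | Yes, at least 2 swollen of 44 | No |
| Enough alone for a primary event | Yes | Yes |
| Decided by unblinded persons | In part (PGA enters DAS28-CRP) | Entirely |
| Same rule in both arms | Yes | No (TNFi increase counts in Standard of care only) |

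**2. How far PGA reaches.** The formula in 8.2.1 gives PGA a weight of 0.014 per mm. With all else unchanged, PGA must rise by more than 0.6/0.014 = 42.9 mm under the 0.6 rule, or 1.2/0.014 = 85.7 mm under the 1.2 rule. At least 2 swollen joints must be found as well. Those joints need not be new. With 1 tender joint, 2 swollen joints and CRP 5 mg/L throughout:

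- PGA 10: 0.56·√1 + 0.28·√2 + 0.36·ln 5 + 0.14 + 0.96 = 2.64
- PGA 60: the same with 0.84 in place of 0.14 = 3.34, a rise of 0.70 to above 3.2, which is a formal flare

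So PGA can tip the threshold, but only where the swollen-joint condition is also met.

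**3. The plan's own figure.** Table 2, 72.5% against 85%, two-sided 5%, 80% power:

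n per arm = (1.960 + 0.842)² × (0.725·0.275 + 0.85·0.15)/0.125² = 7.85 × 0.3269/0.01563 = 164.2, rounded up to 165, total **330**, as stated. The same formula gives the stated 440 at 90% power.

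**4. Size, by assumption only.** The documents give neither the share *s* of flares that are consensus-only nor the fraction *r* of those that would go uncalled in the TDM arm. Suppose no true effect, 72.5% control in both arms and 175 per arm. Apparent control in TDM is then 1 − 0.275(1 − s·r), and the spurious difference is d = 0.275·s·r. The chance of a false superiority claim is 1 − Φ((1.96·SE₀ − d)/SE₁), with SE₀ pooled and SE₁ unpooled. Nominal is 2.5%.

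| s | r = 10% | r = 25% | r = 50% |
|---|---|---|---|
| 20% | 0.6 points, 3.3% | 1.4 points, 4.7% | 2.8 points, 8.5% |
| 40% | 1.1 points, 4.2% | 2.8 points, 8.5% | 5.5 points, 22.1% |
| 60% | 1.7 points, 5.4% | 4.1 points, 14.1% | 8.3 points, 44.5% |

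For s = 40%, r = 25%: d = 0.275 × 0.10 = 0.0275, SE₀ ≈ SE₁ ≈ 0.047, so (0.0921 − 0.0275)/0.047 ≈ 1.375, giving 8.5%. The table shows how the result depends on two unknowns. It is not an estimate for this trial.

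**5. What a formal-only analysis can carry.** If consensus flares drop out and both flare risks shrink by the same factor, power at 350 (no drop-out) falls from about 82% to:

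- s = 20%: 22% against 12% flare, about 70%
- s = 40%: 16.5% against 9%, about 56%
- s = 60%: 11% against 6%, about 39%

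**The case against.** **The SAP may hold this analysis.** Section 9 calls itself a summary, defers detail to the SAP, and leaves the list in 9.3.2.2 open. Component analyses of a composite endpoint are usual SAP content. This stands in part: a reader might infer that no such analysis is planned at all, and the documents do not support that. What remains is that the protocol itself fixes an event rule that differs by arm and a safeguard that misses one route, and names no analysis addressing either.

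**The limit is disclosed.** The protocol says openly that masking covers only part of the outcome. That is so, and nothing is misstated. Disclosure does not show how far the result depends on the unmasked part.

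**PGA.** A reader might infer that PGA is a second unblinded route of its own. It is not, because at least 2 swollen joints on the blinded count are always also required. The example above needs two swollen joints already present and a 50 mm jump. The documents do not say how many participants enter with two swollen joints. Holding PGA at baseline would be no remedy: it makes a non-standard index and leaves in tenderness, which the participant also reports.

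**Other blinded or laboratory evidence exists.** The 44-joint count, CRP and ESR are secondary measures (section 3), and flare measures are an exploratory objective. So it would go too far to say that a benefit could not be told apart from expectation bias. These measures still do not re-estimate the primary contrast on formal flares.

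**The one-arm trigger is deliberate.** Dose increases are part of the TDM intervention, so counting them all as flares would penalize that arm. This explains the rule, but does not show what the rule contributes to the difference.

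**Conclusion.** The point holds for the consensus route. It is sufficient alone, decided by unblinded persons, and contains a trigger that counts in the Standard of care group only. The sensitivity analyses named in the protocol address missing data and covariates, and the supplementary and subgroup analyses use the same composite flare. PGA is a lesser concern.

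The direction of the one-arm trigger favors TDM and follows from the rule as written. The size of any bias cannot be computed, because the documents give no share of consensus flares. The ranges above rest on assumed shares of 20–60% and assumed under-calling of 10–50%. The conclusion concerns this protocol only, since the SAP is not at hand. It is worth correcting before results are known, but does not invalidate the primary analysis.

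**What to change.** Add to 9.3.2.2, with confidence intervals and no p value in line with 9.1.1:

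1. **Formal flares only.** Repeat the primary comparison counting only flares that meet the DAS28-CRP plus 44-joint criterion at any visit over the full 18 months. Include visits after a consensus flare, since sections 4.1 and 6.1.3 keep those participants on the visit schedule. Add a variant that treats formal-flare status after a consensus-only flare as missing and handles it under the planned multiple imputation. The variant is needed because a treatment change after a consensus flare can prevent a later formal one, and scoring such a participant as controlled may be misleading.
2. **Without the one-arm trigger.** Repeat the primary comparison not counting consensus flares whose only major change was the TNFi increase that counts in the Standard of care group alone.
3. **Description.** Report flares by route, qualifying treatment change and arm.

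The cost is a few extra model runs. Consensus flares, RA medication changes and injection dates are already to be recorded (8.2.2, 6.9.2, 6.5). The sponsor should confirm that the flare record identifies the qualifying change. The downside is fewer events and wider intervals, so these analyses are supportive, and a null result in them would not by itself overturn the primary finding.
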